5.2. Dosing Delays and Modifications for Toxicity

5.2.1. Dosing Delays for Hematologic Toxicity

If a patient develops critical drug induced neutropenia or thrombocytopenia (as defined in sections 5.22), 5AC and GM-CSF will be held. If neutrophil count rises to $100-500/\text{mm}^3$, or platelet count rises to $10,000-50,000/\text{mm}^3$, the patient may resume the next cycle at the next lower dose level. If the neutrophil count is greater than $500/\text{mm}^3$ or the platelet count greater than $50,000/\text{mm}^3$, the patient may resume the next cycle at the same dose level. If there is inadequate peripheral count recovery within 56 days from the first day of the most recent cycle the patient will be removed from the study and a bone marrow biopsy and aspirate will be performed.

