3.1. Inclusion Criteria

1. Age \geq 0.5 years
2. Initial diagnosis of poor -risk AML or MDS (defined in section 3.2), treated with either stem cell transplant or consolidation chemotherapy, within the past 60-185 days
3. ECOG performance status 0-2
4. No morphologic evidence of leukemia or active MDS as determined by JHH Hematopathologist independent review of a bone marrow aspirate and biopsy done following the completion of therapy.
5. Peripheral blood count recovery: Neutrophil count \geq 1000 / μ L, platelet count \geq 50x 10⁹ / μ L without platelet transfusions, and adequate hematocrit independent of red cell transfusions .
6. No evidence of extramedullary leukemia, such as CNS or soft tissue involvement
7. Adequate end organ function as measured by the following: AST and ALT \leq 4 x normal, total serum bilirubin $<$ 2 x upper limit normal (unless due to hemolysis, Gilbert's syndrome, or ineffective erythropoiesis), creatinine \leq 2 x upper limit of normal
8. Ability to give informed consent
9. In agreement to use an effective barrier method of birth control to avoid pregnancy during the study and for a minimum of 30 days after study treatment, for all male and female patients who are fertile

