5.1. Treatment Schedule

The planned initial dose of 5AC is $37.5\text{mg}/\text{m}^2$ (Level 0) and this will be administered subcutaneously or intravenously for days 1 through 5 of a 28 day cycle. Patients who tolerate the combination with no SAEs during two consecutive cycles will be eligible for a dose escalation to $50\text{mg}/\text{m}^2/\text{day}$ for 5 days of every 28 day cycle (Level +1). Patients who tolerate Dose Level +1 with no SAEs during two consecutive cycles will be eligible for a dose escalation to $75\text{mg}/\text{m}^2/\text{day}$ for 5 days of every 28 day cycle (Level +2). Patients will

continue at Dose Level +2 for the study’s duration provided there are no toxicities requiring dosing delays or dose reduction.

Dose reductions are permitted as per the standard treatment approach with 5AC and are listed below in Table 2. Patients who experience toxicity or dosing delays, but return to pre-therapy baseline within 56 days of the first day of their most recent cycle, will be eligible to continue at the next lower Dose Level (Table 2). Patients unable to tolerate the lowest dose of 12.5mg/m² /day for 5 days (Dose Level -2) due to toxicities or cytopenias, will be removed from the study. Patients requiring a dose reduction are not eligible for re-escalation. Azacitidine dosing is the same regardless of subject age.

Table 2

Dose Level	5AC
-2	12.5mg/m ²
-1	25mg/m ²
0	37.5mg/m² (starting dose level)
+1	50mg/m ²
+2	75mg/ m ²

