5.2.2. Definitions of Hematologic Toxicity

Critical neutropenia or thrombocytopenia is defined by a neutrophil count $<100/\text{mm}^3$ or a platelet count $<10,000/\text{mm}^3$. Persistent critical cytopenias are those that last for greater than 3 weeks.

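### The 'or' in Section 5.2.1 lets one recovered count justify same-dose resumption while the other is still low, and escalation in Section 5.1 carries no blood-count condition

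*Combined protocol and SAP*

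**What the plan says.** **Hold.** Section 5.2.1: "If a patient develops critical drug induced neutropenia or thrombocytopenia (as defined in sections 5.22), 5AC and GM-CSF will be held". Section 5.2.2 supplies the limits: "Critical neutropenia or thrombocytopenia is defined by a neutrophil count" below 100/mm³ or a platelet count below 10,000/mm³.

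**Resumption.** Section 5.2.1 has two sentences.
- If neutrophils rise to 100-500/mm³, *or* platelets rise to 10,000-50,000/mm³, "the patient may resume the next cycle at the next lower dose level".
- If neutrophils are above 500/mm³, *or* platelets are above 50,000/mm³, "the patient may resume the next cycle at the same dose level".

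Inadequate recovery within 56 days of the start of the latest cycle leads to removal and a marrow examination.

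**Escalation.** Section 5.1 moves a patient from 37.5 to 50 mg/m² after two tolerated cycles without an SAE. It then says: "Patients who tolerate Dose Level +1 with no SAEs during two consecutive cycles will be eligible for a dose escalation to" 75 mg/m². Neither sentence names a count.

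**General toxicity rule.** Section 5.1 also says that patients with toxicity or delays who "return to pre-therapy baseline within 56 days of the first day of their most recent cycle" may continue one level lower, and adds: "Patients requiring a dose reduction are not eligible for re-escalation".

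**Entry and monitoring.** Section 3.1 item 5 ("Peripheral blood count recovery: Neutrophil count") sets a neutrophil minimum of 1000/µL and a platelet minimum read here as 50,000/mm³. Table 4 schedules a CBC before treatment, weekly in cycle 1, on Day 1 of each cycle and at end of treatment.

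**The concern.** After a critical hold, the dose decision depends on two counts that need not recover together. Joining the same-dose thresholds with 'or' means that the better count can settle the matter. A patient held for thrombocytopenia will often have neutrophils above 500 throughout, because they were never the problem, and so meets the same-dose sentence whatever the platelets are doing. A rule meant to test recovery then tests nothing.

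Two things are at stake. One is safety: full-dose azacitidine could be resumed with a count that the same section treats as grounds for a reduction, or even for a hold. The other is uniformity: two investigators with identical counts could choose different levels and both comply, and the lower choice cannot be reversed.

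Escalation raises a related but separate question. The dose can double without any stated count. The plan relies on its dosing rules: Section 7.2.1 presents them as supporting patient safety, and Section 9.4 cites dose adjustment among its reasons for accepting lenient futility stopping.

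**Working it through.** The plan states no figure to reproduce. The check applies the Section 5.2.1 sentences to specific patients, keeping the condition that the lower-dose sentence requires a count to have *risen* from a critical value.

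| Patient under a critical hold | Hold still applies? | Lower-dose sentence met? | Same-dose sentence met? | Under the proposed wording |
|---|---|---|---|---|
| A. Platelets were critical, now 30,000; neutrophils 1500 | No | Yes (platelets) | Yes (neutrophils) | Lower |
| B. Neutrophils were critical, now 300; platelets 80,000 | No | Yes (neutrophils) | Yes (platelets) | Lower |
| C. Platelets still below 10,000; neutrophils above 500, never critical | Yes | No | Yes (neutrophils) | Hold |
| D. Neutrophils still below 100; platelets above 50,000, never critical | Yes | No | Yes (platelets) | Hold |
| E. Both were critical; neutrophils now 1500, platelets 30,000 | No | Yes (platelets) | Yes (neutrophils) | Lower |

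**Narrower reading.** Suppose each sentence refers only to whichever count was critical. A and B then give the lower dose, and C and D give a hold. E remains unresolved: the neutrophils point to the same level and the platelets to the lower one. Nothing in Section 5.2.1 or 5.2.2 states this reading or says which count decides in E.

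**Size of the dosing difference in A, B and E**, from Table 2 (same level divided by next lower level):
- Level +2: 75/50 = 1.5
- Level +1: 50/37.5 = 1.33
- Level 0: 37.5/25 = 1.5
- Level -1: 25/12.5 = 2.0

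At Level -2 there is no lower level.

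**Escalation.** With two qualifying cycles at each step, Level 0 covers cycles 1-2, Level +1 can start at cycle 3 and Level +2 at cycle 5. An escalated dose is therefore possible in cycles 3-12, which is 10 of the 12 planned. The top level is 75/37.5 = 2 times the starting dose. None of the seven SAE items in Section 10.5 is a blood count, and the requirement to tolerate treatment is not defined by one. The Section 5.3 rule for starting a cycle sets a 28-to-56-day window, again without a count.

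**The case against.** The strongest reply is that sensible clinicians will not be misled. In C and D a mandatory hold meets a permissive resumption, so the hold naturally prevails. In A and B, judging each count by its own cytopenia is the ordinary reading. Both points have force. But A, B and E set two permissive sentences against each other, so mandatory-over-permissive does not settle them, and the ordinary reading is unwritten and leaves E open.

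Three stronger inferences are tempting, and the documents do not support them.

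- *A first-seen, non-critical low count on Day 1 (say neutrophils of 150) is controlled by nothing but judgement, and such a patient may simply be escalated.* Section 5.1's general toxicity rule points such a patient towards recovery to baseline and then a lower level. Section 7.4 lists neutropenia and thrombocytopenia among the drug's toxicities. Escalation makes a patient only eligible, and Section 5.3 allows the physician to stop treatment. Section 5.6 lets the testing schedule change with the patient's condition, and Section 6.1 sends recurrent cytopenias to marrow examination. The protection is partial, because none of this sets a count for escalation, but it exists.
- *Most combinations of count bands give contradictory instructions.* That follows only if the requirement for a rise from a critical value is ignored. Unweighted combinations also say nothing about how often patients fall in them.
- *Sections 5.1 and 5.2.1 contradict each other irreconcilably over return to baseline.* The ordinary resolution is that 5.2.1 is the specific rule for critical blood counts and 5.1 the general one.

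**Conclusion.** The point holds as a defect in a stated dosing rule. Read literally, Section 5.2.1 permits same-dose resumption when the other count is still in its reduction band, and its same-dose sentence is met even while the other count is critical. On the narrower reading the conflict is confined to patients with both counts critical and unequal recovery. No other section corrects the wording. Where the conflict arises, the two permitted doses differ by a factor of 1.33 to 2, and the lower choice is permanent.

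The missing count in the escalation sentences is a secondary gap, partly covered by the safeguards above.

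The conclusion assumes that the entry platelet minimum means 50,000/mm³ and that 5.2.1 governs critical blood counts. The documents do not say how often these count patterns occur, so the number of affected patients is unknown. A reader might infer damage to the primary RFS analysis. Nothing in the documents shows that, and the point concerns patient safety and uniform dosing only.

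**What to change.** **1. Section 5.2.1.** Keep the opening hold and the 56-day removal rule. Replace the two resumption sentences with: 'Same dose level: neutrophils above 500/mm³ AND platelets above 50,000/mm³. Next lower dose level: neither count critical, but at least one in its lower band (neutrophils 100-500/mm³ or platelets 10,000-50,000/mm³). While either count is critical, both drugs stay held.' Resumption stays permissive, as now.

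**2. Section 5.1.** Add to both escalation sentences: 'and Day 1 neutrophils above 500/mm³ and platelets of at least 50,000/mm³.' Using *at least* for platelets avoids barring a stable patient who entered exactly at the minimum. The neutrophil floor is still below the entry minimum of 1000. It borrows the protocol's own resumption threshold, and the sponsor may prefer a higher one.

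**3. Leave unchanged** Section 5.1's return-to-baseline rule for non-critical cytopenias. Overriding it would loosen the current text.

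**Cost.** A wording amendment to two sections. The Day 1 CBC is already in Table 4, so no test is added. A few more patients may be reduced, permanently under Section 5.1, and a few escalations deferred.

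### The haematologic resume rules in Section 5.2.1 do not say how neutrophils and platelets combine, so the same counts can qualify for two different dose levels

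*Combined protocol and SAP*

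**What the plan says.** Section 5.2.1 starts with the hold: "If a patient develops critical drug induced neutropenia or thrombocytopenia", both 5AC and GM-CSF are held. Section 5.2.2 supplies the limits: "Critical neutropenia or thrombocytopenia is defined by a neutrophil count" below 100/mm³ or a platelet count below 10,000/mm³.

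Section 5.2.1 then gives two ways back, each with its neutrophil and platelet conditions joined by 'or':

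- Neutrophils rise to 100-500/mm³ or platelets rise to 10,000-50,000/mm³: "the patient may resume the next cycle at the next lower dose level".
- Neutrophils exceed 500/mm³ or platelets exceed 50,000/mm³: "the patient may resume the next cycle at the same dose level".

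A patient without adequate recovery by 56 days from the first day of the cycle leaves the study. Adequate recovery is not defined by count or by lineage.

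Section 5.1 has its own rule. A patient with toxicity or a dosing delay who is back at baseline within the same 56 days is eligible to continue one level down. It also states that a reduced dose cannot be raised again.

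**The concern.** A dose-modification rule should give one action for one set of counts. Here two conditions that can hold together point to different levels, and no order of precedence is given. The hold begins when either lineage is critical, yet the wording lets recovery in either lineage end it.

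Two features of the plan give this weight. Because re-escalation is barred after a reduction, a single choice of level carries through the rest of the 12 planned cycles (Section 5.3). And Section 9.4 accepts lenient futility rules partly on the ground that toxicity is monitored and doses are adjusted to it, which presumes an adjustment rule with one outcome.

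**Working it through.** The plan gives no figure to reproduce; the check is an enumeration.

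**Inputs.** Hold trigger and resume bands from Section 5.2.1; critical limits from Section 5.2.2; baseline rule and bar on re-escalation from Section 5.1.

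**Conditions as written** (N = neutrophils/mm³, P = platelets/mm³):

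- Lower level: 100 ≤ N ≤ 500 or 10,000 ≤ P ≤ 50,000
- Same level: N > 500 or P > 50,000
- Critical: N < 100 or P < 10,000

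**Result.** Three bands per lineage give 3 × 3 = 9 combinations:

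| | P < 10,000 | P 10,000-50,000 | P > 50,000 |
|---|---|---|---|
| N < 100 | neither rule met | lower, N still critical | same, N still critical |
| N 100-500 | lower, P still critical | lower | **lower and same** |
| N > 500 | same, P still critical | **lower and same** | same |

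- Both rules met: 2 of 9. Example: N = 300, P = 80,000.
- Resumption allowed with one lineage critical: 4 of 9, two at the same level and two at the lower level. Example: N = 99, P = 50,001 meets the same-level rule.
- One outcome consistent with Section 5.2.2: 9 − 2 − 4 = 3 of 9.

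**How the count changes under narrower readings:**

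| Reading | Patients | Both rules met | Resume while critical |
|---|---|---|---|
| Literal | any held patient | 2 | 4 |
| Hold prevails until no lineage is critical | any held patient | 2 | 0 |
| Only the triggering lineage counts | one lineage was critical | 0 | 0 |
| Only the triggering lineage counts | both were critical | 2 | 4 |
| Both narrower readings together | both were critical | 2 | 0 |

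Under the triggering-lineage reading, a single-lineage hold has three bands and one outcome for each. If both lineages triggered the hold, both count and the full grid returns. The two double-outcome cells therefore survive every reading for patients in whom both lineages became critical.

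**Changing the conjunction.** As a logic check only, putting 'and' for 'or' in both rules removes all 2 + 4 conflicts. But 7 of 9 combinations then meet neither rule, including the two mixed ones in which no lineage is critical. A change of one word does not complete the rule.

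**Against Section 5.1.** Entry requires neutrophils of at least 1000 (Section 3.1). A patient back at a baseline of that order has N > 500 and so meets the same-level rule of Section 5.2.1, while Section 5.1 names the next lower level. Even the lower right cell, which is clear within Section 5.2.1, is not clear once Section 5.1 is read with it.

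**The case against.** The best defence is that the rules are meant lineage by lineage. The hold sentence names neutropenia or thrombocytopenia, and the resume sentences follow the same pairing. 'Rises to' in the lower-level rule presupposes a count that had fallen. On that reading, a patient held for platelets whose neutrophils never fell does not meet the same-level rule through the neutrophils. This would settle many single-lineage cases. But the protocol does not state it, the same-level rule says only that the count is greater than its limit, and a conflict remains when both lineages were critical and recover to different bands.

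A second defence is that the hold is mandatory and resumption only permitted ('may'), so the hold should prevail while any lineage is critical. That is a fair reading and would clear the four critical cells. It too is unstated, and it does nothing for the two cells with two outcomes: an investigator may decline to resume, but that does not settle the level. The 56-day removal rule does not help either, since adequate recovery is undefined.

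Section 5.2.1 could also be taken as the specific rule that displaces Section 5.1 for cytopenias. The text does not say so.

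A reader might infer that the toxicity description, a secondary objective, would depend on who reads the rule. The documents do not support that: adverse events are graded by CTC weekly in the first cycle and at least every cycle afterwards (Sections 10.2 and 10.6), whichever rule is used. What can vary is the dose received.

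**Conclusion.** This is an internal inconsistency that should be corrected. On the literal text, 2 of 9 count combinations qualify for two dose levels and 4 of 9 permit resumption with a lineage still critical. These counts assume that the rules apply without regard to which lineage caused the hold. On the most favourable combination of unstated readings, the conflict within Section 5.2.1 shrinks to the two mixed cells in patients who were critical in both lineages. The disagreement with Section 5.1 remains unless one section is declared to govern.

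Two stronger inferences are not supported. First, 6 of 9 combinations does not mean that two thirds of held patients are affected: the cells are unweighted, and the documents give no frequency for such counts in this population. Second, the protocol does not clearly authorise dosing during a critical cytopenia: the literal wording permits it, but the mandatory hold points the other way. Sample size, the futility design and the GVHD stopping rule are untouched. The consequence is that identical counts can lead to different dose levels, and a reduction cannot be reversed.

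**What to change.** Reconcile Sections 5.1, 5.2.1 and 5.2.2 so that each pair of neutrophil and platelet counts leads to exactly one action. The text should state:

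- how the two lineages combine, and whether only the lineage that caused the hold counts;
- when the hold ends;
- whether Section 5.1 or Section 5.2.1 governs after a haematologic delay;
- what counts as adequate recovery for the 56-day removal rule.

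A table of the nine combinations with one action in each would be enough, and would show at once whether any cell is empty or doubly filled. Which action belongs in each cell is for the sponsor's clinicians.

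The cost is a short amendment: one rewritten paragraph in Section 5.2.1 and a matching sentence in Section 5.1. No statistical design figure needs to be recalculated.

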5.2.2. Definitions of Hematologic Toxicity

Critical neutropenia or thrombocytopenia is defined by a neutrophil count $<100/\text{mm}^3$ or a platelet count $<10,000/\text{mm}^3$. Persistent critical cytopenias are those that last for greater than 3 weeks.

5.2.3. GVHD

If a patient develops clinical grade 3 or 4 acute GVHD⁵³, study therapy will be held until GVHD has stabilized or resolved. Patients who develop clinical Grade 2 GVHD may continue on therapy with close observation (typically clinic visits 2-3 times / week), but will have study therapy held for advancing GVHD. Study therapy will be held should a patient develop Severe chronic GVHD until stabilization or resolution. If a patient develops mild or moderate chronic GVHD⁵⁴, the patient may continue on therapy with close observation (typically clinic visits 2-3 times per week), but study therapy must be held for advancing or uncontrolled GVHD.

5.2.4. Non-hematologic Adverse Events

Patients with grade 3 or 4 non-hematological adverse event, deemed by the investigator to be possibly, probably or definitely related to the study drugs, will hold both 5AC and GM-CSF through the start of the next planned cycle. If the adverse events resolve to pre-treatment baseline, the study drugs will be resumed starting with the following scheduled cycle at the next lowest Dose Level. To allow for resolution of adverse events, patients may have study drugs held for up to 58 days from the start of the most recent cycle prior to being removed from the study.

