GM-CSF will be self-administered subcutaneously for days 1-10 of each 28 day cycle. For subjects unable to self-administer, GM-CSF may be administered by a caregiver or on site at Johns Hopkins or a local provider’s office. Dosing will be based on weight and rounded to a standard dosing size: patients who weigh less than or equal to 70kg will receive 125 micrograms/day and those who weigh over 70kg will receive 250 micrograms/day. Pediatric subjects will receive 125 micrograms/day regardless of weight. Subjects will be given prescriptions for pre-dosed syringes of GM-CSF. If the starting dose is not tolerated due to traditional side effects of GM-CSF, such as muscle aches and pains, bone or joint discomfort, or elevated WBC > 25,000, the drug will be held through resolution of these side effects. Patients who return to their pre-dosing baseline will re-start the GM-CSF at the next cycle start date at the next lower Dose Level (Table 3). Patients unable to tolerate the minimum dose (Dose Level -3) for 7 days due to either persistently elevated WBC or other side effects will be removed from the study.

Table 3

Dose Level	GM-CSF patients >18 years	Patients ≤ 18 years
-3	50micrograms x 7 D	50micrograms/ m ² x 7D
-2	50 micrograms x10 D	50micrograms/ m ² x 10D
-1	62.5 micrograms x 10D	62.5micrograms/ m ² x10D
0	125 micrograms (starting dose weight <70 kg) x 10D	125micrograms/ m² x10D¹
+1	250 micrograms (starting dose weight >70 kg) x 10D	

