7.1.2. Drug Combination

As to the safety of the combination, GM-CSF is often used as standard supportive care in patients receiving 5AC and tolerated well. Therefore, we do not expect increased toxicity from the combination. In fact, GM-CSF may mitigate the myelosuppressive effects of 5AC.

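### Sections 5.1 and 5.2.4 give different dosing instructions for the same grade 3 or 4 GM-CSF-type reaction, and 5.2.1 and 5.2.4 do not say which drug's dose level is lowered

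*Combined protocol and SAP*

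**What the plan says.** The two drugs have separate dose-level tables that share level names: Table 2 for 5AC (levels -2 to +2) and Table 3 for GM-CSF (levels -3 to +1).

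- **5.1, 5AC paragraph.** "Patients who experience toxicity or dosing delays" and recover to baseline within 56 days "will be eligible to continue at the next lower Dose Level (Table 2"). The causal drug is not specified. The same paragraph adds: "Patients requiring a dose reduction are not eligible for re-escalation".
- **5.1, GM-CSF paragraph.** For typical GM-CSF side effects, "such as muscle aches and pains, bone or joint discomfort, or elevated WBC > 25,000", GM-CSF is held until they resolve. "Patients who return to their pre-dosing baseline will re-start the GM-CSF at the next cycle start date at the next lower Dose Level", here with Table 3 cited. Nothing is said about 5AC.
- **5.2.1, critical cytopenia.** Both drugs are held. On partial count recovery "the patient may resume the next cycle at the next lower dose level". No drug or table is named.
- **5.2.4, related grade 3 or 4 non-hematologic events.** The patient "will hold both 5AC and GM-CSF through the start of the next planned cycle". If the event resolves to baseline, the study drugs (plural) restart with the scheduled cycle after that, one level lower. No table is named.
- **5.3.** Treatment ends if either drug cannot be tolerated at its lowest level (item 7), or if dosing is delayed beyond 56 days from the start of the most recent cycle (item 6).

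**The concern.** A severe muscle or bone pain judged related to treatment is a GM-CSF side effect under 5.1 and a related grade 3 or 4 non-hematologic event under 5.2.4. The two rules differ on what is held, what is reduced and when dosing restarts, and neither says it overrides the other. Attribution may not settle the matter: myalgia is listed as a toxicity of 5AC (7.4) and of GM-CSF (7.5), and 5.2.4 applies even when the relationship is only possible.

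At stake is consistent dosing. Two investigators following the protocol could give different doses after the same event, and a resulting 5AC reduction is permanent. Toxicity of the combination is a secondary objective, and section 10.1 requires reporting on protocol compliance and treatment administration. Compliance is hard to audit against a rule with several readings.

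**Working it through.** The plan states no figure on this point, so the check sets the rules side by side and then does arithmetic on Tables 2 and 3.

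**One event.** Take a related grade 3 bone pain that resolves to baseline in a patient at 5AC Level 0 (37.5 mg/m2):

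| Rule applied | Held | Table stepped down | Restart | 5AC afterwards |
|---|---|---|---|---|
| 5.1, GM-CSF paragraph alone | GM-CSF | Table 3 | next cycle start | 37.5 (no instruction) |
| 5.2.4, read for both tables | both drugs | Tables 2 and 3 | cycle after the next planned one | 25 |
| 5.2.4, read for Table 2 only | both drugs | Table 2 | same | 25 |
| 5.2.4, read for Table 3 only | both drugs | Table 3 | same | 37.5 |

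The plural in 5.2.4 favors the second row, but the text does not exclude the third and fourth. The first row is also not secure. The 5AC paragraph of 5.1 is triggered by toxicity from either drug, so it could bring 5AC down to 25 even if 5.2.4 were set aside.

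**Size of one step.** 5AC from Level 0 to Level -1: (37.5 - 25)/37.5 = 33%. The next step, to Level -2: (25 - 12.5)/25 = 50%.

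**Running out of levels.** This assumes repeated, separate events of this kind in an adult who stays at 5AC Level 0 until the first of them.

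- If each event lowers both drugs, 5AC goes 37.5, 25, 12.5, and no 5AC level is left at the third event.
- If each event lowers GM-CSF only, there are three levels below Table 3 Level 0 and four below Level +1. Levels run out at the fourth event (starting at 0) or the fifth (starting at +1).

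Item 7 of 5.3 then ends treatment, so the reading chosen can affect when a patient stops.

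**Timing.** If 5.2.4 means that the next planned cycle is missed, restart falls at 28 + 28 = 56 days from the start of the most recent cycle. That is exactly the limit in 5.3, whereas 5.2.4 allows a hold of 58 days. This is one reading of the restart wording, but the 56 and 58 days differ on any reading.

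**Cytopenia (5.2.1).** No table is named. The 5AC paragraph of 5.1 uses the same 56-day window, steps down on Table 2 and mentions cytopenias at the lowest 5AC level. The Table 3 triggers in 5.1 are GM-CSF side effects and a high white count, never low counts. Table 2 is therefore the more natural reading, but 5.2.1 does not say so.

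**The case against.** The best defense is that the rules form a severity ladder: 5.1 for familiar GM-CSF side effects that are not tolerated, 5.2.4 for related grade 3 or 4 events. Holding and reducing both drugs after a severe event would then be a coherent choice. That reading is plausible, and it narrows the overlap: reactions below grade 3 do not reach 5.2.4, and a white count above 25,000 is hematologic and falls outside it. But the protocol does not state the ladder, and even if 5.2.4 governs, it still names no table.

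The defense is right against several stronger claims that a reader might infer:

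- *Dose levels are never tied to a drug.* Section 5.1 cites Table 2 and Table 3 explicitly. The gap is in 5.2.1 and 5.2.4.
- *A cytopenia will lead to a GM-CSF cut, against the plan's own rationale.* This needs the less natural reading of 5.2.1. Section 7.1.2 says only that "GM-CSF may mitigate the myelosuppressive effects of 5AC", which does not settle how 5.2.1 should be read.
- *GM-CSF reductions are irreversible.* The bar on re-escalation stands in the 5AC paragraph, and nothing extends it to Table 3.
- *The relapse-free survival result is compromised.* Individual dose adjustment is part of the design, relapse-free survival is estimated per cohort whatever the dose, and the documents give no frequency for these events. Section 7.5 describes GM-CSF effects as generally tolerated. No effect on the endpoint can be sized.

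**Conclusion.** The concern holds in limited form. For a related grade 3 or 4 GM-CSF-type reaction such as muscle or bone pain, 5.1 and 5.2.4 conflict on what is held, what is reduced and when dosing restarts. At 5AC Level 0 the difference is 37.5 against 25 mg/m2 (33%) after one event, with no way back up for 5AC once reduced. Section 5.2.1 has a milder version of the same gap.

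The 33% assumes that 5.2.4 applies to Table 2, and that the 5AC paragraph of 5.1 is not also triggered under the other rule. The event counts assume repeated reactions, whose likelihood the documents do not give. The finding does not say which dosing rule is correct, and it makes no claim that GM-CSF reductions are permanent or that relapse-free survival is affected by any stated amount.

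**What to change.** Reconcile 5.1, 5.2.1, 5.2.4 and 5.3 in one wording amendment:

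1. In 5.2.1 and 5.2.4, name the drug and table (5AC/Table 2, GM-CSF/Table 3, or both) to which each dose-level step applies.
2. State which rule governs when an event meets both the GM-CSF paragraph of 5.1 and 5.2.4, including what is held and at which cycle each drug restarts.
3. In the 5AC paragraph of 5.1, say whether toxicity attributed to GM-CSF alone counts as a trigger.
4. Make the maximum hold in 5.2.4 (58 days) agree with 5.1, 5.2.1 and 5.3 (56 days).

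The clinical team decides which rule stands in each case. The cost is an amendment with the IRB approval that section 11.1 requires. It adds no patients, visits or analyses.
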